5.2.2.2. Sensitivity Estimators of the Main Estimand

Sensitivity analyses will be conducted by constructing three sensitivity estimators for the primary estimand as defined in Section 5.2.2. One estimator will test the assumption of homogeneous treatment effect across the 2 randomization stratification factors, and the 2 other ones will use different missing data imputation rules.

5.2.2.2.1. Sensitivity Estimator 1 For the Main Estimand (Homogeneity Assumption)

Homogeneity will be assessed for scientific question part b, comparison vs control arm. For this sensitivity estimator 1, the same included data, missing data assumption (MAR), and missing data handling rule (multiple imputation) as well as the same approach to control the Type I error rate (Section 5.1.1) will be applied. The assumption for homogeneity of treatment effect across the stratification factors will be tested and, if heterogeneity is found statistically significant, a different statistical model is used to define the sensitivity estimator.

5.2.2.2.1.1. Assumptions

- Missing Data for HBV RNA, ALT, and HBsAg are Missing at Random
- The treatment effect is non-homogeneous across strata

5.2.2.2.1.2. Analysis Methods

Homogeneity of treatment effect for each stratification factor separately will be tested using the weighted least squares chi-squared statistic (Lui K. J. et al., 2000) for one-way homogeneity. Tests of homogeneity will be assessed at the one-sided 10% level of significance.

Any heterogeneity found to be statistically significant will be explored using the following statistical model for the sensitivity estimator 1.

Statistical model: A logistic regression model on the primary efficacy endpoint using the 2 randomization stratification factors and interaction terms. The model will include intervention arm, treatment history status and HBeAg status at screening as factors, and the intervention arm-by-factor interaction terms.

5.2.2.2.2. Sensitivity Estimator 2 For the Main Estimand (LOCF)

For this sensitivity estimator 2, the same statistical model (MCP-Mod and stratum-adjusted MH test), data included and approach to control the Type I error rate will be used as for the main

estimator (Section 5.2.2.1). The assumption for missing data and the rule to handle missing data have changed.

5.2.2.2.1. Assumptions

- Missing Data for HBV RNA, ALT, and HBsAg are Missing Completely at Random (Barnes A. et al., 2008)
- The treatment effect is homogeneous across strata

5.2.2.2.2. Missing Data Handling Rule

For sensitivity estimator 2, participants who withdraw from the study prior to Week 48 will be considered as non-responders. After taking into account all the intercurrent events and applying the intercurrent event strategies specified in Section 5.2.2, if a subject who did not experience any ICEs has missing response status for the primary efficacy endpoint then the LOCF approach will be used as follows.

If any of the lab parameters values (used to define response status per primary efficacy endpoint) are missing at Week 44, the Last Observation Carried Forward (LOCF). The non-missing value closest to Week 44 will be selected among the non-missing values which are no earlier than 4 weeks prior. The imputed values will be chosen to be all at the same timepoint. If 2 non-missing laboratory values are equidistant, the later observation will be preferred.

For Mod-step, model averaging techniques across the statistically significant candidate models obtained from the MCP step will be used to derive the dose-response shape (Mod step).

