9.4. Statistical Analyses

9.4.1. Efficacy Analyses

To evaluate the efficacy, the primary analysis set will be the ITT population. Participants will be analyzed according to the study intervention they were randomly assigned to.

All efficacy summaries will be presented with descriptive statistics by intervention arm. If the endpoint is continuous, the descriptive statistics will include the number of participants, mean, standard deviation (SD), median, and range. If the endpoint is binary or categorical, the frequency distribution with the number and percentage of participants in each category will be calculated. For time-to-event variables, a summary table including number of participants included in the analysis, number of participants censored, 25th and 75th percentiles and median time-to event will be shown by intervention arm. Graphic displays will also be used to summarize the data. Summaries will also be presented by randomization stratification factors, HBeAg status at screening and treatment history.

The baseline measurements are defined as the measurements taken closest to but before the first dose of study intervention on Day 1.

Inferential analyses will be specified for each of the endpoints in the following sections. In general, comparisons between intervention arms will be accompanied by appropriate confidence intervals (CIs).

9.4.1.1. Primary Efficacy Endpoint (Proportion of Participants Meeting the NA Treatment Completion Criteria at Week 48)

A hybrid methodology that combines aspects of multiple testing with modeling techniques (MCP-Mod) will be used for evaluating a dose-response trend and estimating the dose-response relationship of 3 JNJ-3989 doses in combination with NA versus NA treatment alone (control Arm 6). Because the primary efficacy endpoint is binary, the generalized MCP-Mod approach will be used on the logit scale. A significant dose-response signal is declared if one or more prespecified models have been found to be significant (multiple contrast test approach). The statistically significant models form a model pool used to estimate the dose-response relationship and select a dose (modeling step).

A set of 5 candidate models (see Figure 2) will be used to cover a suitable range of possible dose-response shapes in terms of the logit of the primary efficacy endpoint, the proportion of participants meeting the NA treatment completion criteria at Week 48.

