5.2.2.1. Main Estimator

5.2.2.1.1. Analysis Methods

5.2.2.1.1.1. Scientific Question Part a: JNJ-3989 Dose Response Trend Test and Dose Response Model Estimation

[figure not shown]
Statistical Model: For the JNJ-3989 dose-finding objective, a hybrid methodology that combines aspects of multiple testing with modeling techniques (MCP-Mod) will be used for evaluating a dose-response trend and estimating the dose-response relationship of 3 JNJ-3989 doses in combination with NA (Arm 2, 3 and 4) versus NA treatment alone (control Arm 6). Because the primary efficacy endpoint is binary, the generalized MCP-Mod approach ([Pinheiro J. et al, 2014](#)) will be used on the logit scale. Following the notation in Pinheiro et al (2014), the “dose-response parameter” estimates and their variance-covariance matrix will be obtained from a logistic regression with JNJ-3989 dose treated as a factor, where Arm 6 corresponds to “JNJ-3989 dose=0

mg”. The Firth's penalized likelihood method (Firth D., 1993 & Heinze G. et al., 2002) will be used in the logistic regression to reduce possible bias which could arise in the presence of a zero response rate at one or more dose levels

If one or more prespecified models are found to be significant (multiple contrast test approach), a significant trend test among Arms 2, 3, 4, and 6 (JNJ-3989 40 mg, 100 mg and 200 mg and NA control), under the null hypothesis of no differences across the 4 arms will be declared.

A set of 5 candidate models (see [Figure 1](#)) was prespecified as possible dose-response shapes in terms of the logit of the primary efficacy endpoint. The 5 candidate models are the EMax1 (ED₅₀=5 mg), EMax2 (ED₅₀=100 mg), Linear, Exponential (d=40) and Sigmoid Emax model (ED₅₀=110 mg, h=8). A dose-response trend is established when the maximum of the t-test statistics exceeds the critical value at the one-sided 0.05 alpha.

Figure 1: Candidate Dose-response Models on the Logit Scale

Characterization of the dose-response model: The model averaging techniques (Bornkamp B. et al., 2009) across the candidate models will be utilized to derive the dose-response shape and to evaluate the desired dose(s) of JNJ-3989 (modeling step). The estimated dose response curve and the corresponding 90% confidence band will be plotted against the JNJ-3989 dose range of 0 mg to 200 mg.

5.2.2.1.1.2. **Scientific Question Part b: Pairwise Comparisons vs Control Arm**

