For Mod-step, model averaging techniques across all 5 candidate models will apply to each imputed dataset and produce the weighted estimates of the treatment effect across the JNJ-3989 dose range (0 mg to 200 mg). The standard errors will be obtained using bootstrapping techniques and then combined into one result using PROC MIANALYZE. The final response estimates on the logit scale for each dose level in the range 0 mg to 200 mg and their 90% CI will be back transformed to the original scale of proportion of responders and plotted with the corresponding 90% confidence band.

For pairwise comparisons of Arms 1 vs 6 and Arm 5 vs 6, as well as the comparisons amongst combination regimens (Arms 1, 3, and 5), the MH test will be performed for each dataset to generate individual estimates of the difference in proportions and the standard error adjusted on

stratification factors. Then the results from these multiple imputed datasets are combined (pooled) for obtaining the overall inference and p-value in a way that accounts for the variability between imputations (Ratitch B. et al., 2013)

Depending on the amount of missing data, the number of imputed datasets to be generated will be increased appropriately from the planned 200 to ensure robustness in the MI results and relative efficiency (Graham JW. et al., 2007).

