5.2.2.2.3. Sensitivity Estimator 3 For the Main Estimand (Tipping Point)

For this sensitivity estimator 3, the same statistical model (MCP-Mod, stratum-adjusted MH test), data included and approach to control the Type I error rate will be used as for the main estimator (Section 5.2.2.1). The assumption for missing data and the rule to handle missing data have changed.

5.2.2.2.3.1. Assumptions

- Missing Data for HBV RNA, ALT, and HBsAg are Missing Not at Random (MNAR)
- The treatment effect is homogeneous across strata

5.2.2.2.3.2. Missing Data Handling Rule

For sensitivity estimator 3, the tipping point approach with the exhaustive scenario's analysis will be applied.

Instead of imputing non-response for missing data, the following method will be utilized to vary the imputation of response for missing data. For participants with missing response data at Week 48, responder status will be imputed in an increasing manner by participant count for each treatment group. Specifically, for each participant with missing primary endpoint at Week 48, a responder/non-responder status will be imputed starting with the scenario where all participants

are non-responders up to the scenario where all participants are responders. This would include all possible scenario combinations of responder/non-responder status for all missing data, including scenarios where participants on any active Arm have worse outcomes than participants on placebo+placebo+NA. Within the exhaustive scenarios list, the ‘worst case scenario’ will be one of the cases where all participants with missing Week 48 data in the active regimen arms will be imputed to ‘non-responders’ and all participants with missing data at Week 48 in the placebo+placebo+NA arm will be imputed to “responders”. For each scenario, the same statistical model (MCP-Mod, stratum-adjusted MH test), will be used as for the main estimator of pairwise comparisons (Section 5.2.2.1.1.2). will be performed. A graphical display of the p-values for the different hypotheses testing will summarize the results across all scenarios for this sensitivity estimator 3.

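### The main dose-response curve averages all five candidate models but the LOCF curve averages only the significant ones, so comparing them mixes a model-pool change with the missing-data change.

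*SAP*

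**What the plan says.** **All five models.** For the main estimator of the primary endpoint, SAP 5.2.2.1.4 says that "model averaging techniques across all 5 candidate models will apply to each imputed dataset". SAP 5.2.2.1.1.1 agrees, stating without a significance filter that averaging "across the candidate models will be utilized to derive the dose-response shape". SAP 5.3.2.1.4 repeats the all-five rule for the key secondary endpoint (functional cure at Week 72).

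**Significant models only.** Protocol 9.4.1.1, and 9.1 in the same terms, says: "The statistically significant models form a model pool used to estimate the dose-response relationship and select a dose (modeling step". The SAP uses this pool in three pairs of analyses:

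- LOCF sensitivity estimators (5.2.2.2.2 and 5.3.2.2.1): "model averaging techniques across the statistically significant candidate models obtained from the MCP step will be used to derive the dose-response shape (Mod step"
- ITT+LOCF supplementary estimators (5.2.2.3.1.2 and 5.3.2.3.2)
- missing-as-non-response analyses (5.2.3.1.1 and 5.3.2.3.4)

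**What LOCF is said to change.** The opening of SAP 5.2.2.2.2 keeps the MCP-Mod model, the data and the Type I error control of the main estimator, and then says: "The assumption for missing data and the rule to handle missing data have changed". The pool change appears two subsections later, under the missing-data heading.

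The SAP gives no reason for the different pools, and its amendment history does not mention them.

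**The concern.** Establishing the dose-response relationship is part of the primary objective, and SAP 5.2.2.1.1.1 uses the Mod step to evaluate the desired dose or doses. A sensitivity analysis of that curve is useful only if it varies the thing it is named for.

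LOCF is the only sensitivity estimator of the primary endpoint with a stated Mod curve. The homogeneity estimator (5.2.2.2.1) concerns the comparisons with control. For the tipping-point estimator (5.2.2.2.3) the planned output is p-values: "A graphical display of the p-values for the different hypotheses testing will summarize the results across all scenarios for this sensitivity estimator 3". So the one planned check of the curve against missing-data handling also changes the model pool. The ITT+LOCF curve differs from the main one in three respects: analysis set, imputation and pool.

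A reader who saw the main and LOCF curves diverge could not tell from those two displays alone how much was due to missing data.

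**Working it through.** **Inputs.** From Protocol 9.2:

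- 45 participants in Arm 6 and 90 each at 40, 100 and 200 mg
- control rate 5%; highest-dose rate 25% (the 20% and 30% rows of Table 6 were also used)
- one-sided alpha 0.05
- five logit-scale shapes: Emax (ED50 5), Emax (ED50 100), linear, sigmoid Emax (ED50 110, h 8), exponential (delta 40)

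Assumptions the documents do not settle: the zero-cell correction behind the power table, the averaging weights (generalized AIC, gAIC), the parameter bounds, and whether contrasts are fixed in advance or recomputed from each dataset's covariance.

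**Step 1: reproduce Table 6.** With contrasts and a multivariate-normal critical value from each dataset's covariance, 0.25 added per cell and 4,000 runs per cell:

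| 25% row | Emax 5 | Emax 100 | Linear | Sigmoid | Exponential |
|---|---|---|---|---|---|
| Protocol | 0.851 | 0.953 | 0.978 | 0.991 | 0.994 |
| Recomputed | 0.859 | 0.942 | 0.978 | 0.992 | 0.994 |

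All 15 cells of the table agree within 2 points. With the Firth correction (0.5 per cell), which the SAP specifies for the analysis, the Emax 5 cell is 0.880, or 2.9 points high. The other four cells of this row are 0.941, 0.977, 0.992 and 0.994.

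**Step 2: why the pools differ.** Take Emax with ED50 5 as the true shape, scaled to 5% at dose 0 and 25% at 200 mg:

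- s(d) = [d/(5+d)] / [200/205], giving s(40) = 0.911 and s(100) = 0.976
- logit p(d) = −2.944 + 1.846 × s(d), giving rates of 5%, 22.1%, 24.2% and 25%
- variances 1/[n p(1−p)] = 0.468, 0.0646, 0.0606 and 0.0593

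A model is significant if T = c′μ / √(c′Sc) exceeds the critical value, 2.015 with fixed contrasts. At the true rates:

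- Emax 5, c = (−0.858, 0.179, 0.315, 0.364): T = 1.541 / √0.3603 = 2.57
- Exponential, c = (−0.194, −0.373, −0.293, 0.859): T = 0.433 / √0.0755 = 1.58

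The trend is then expected to be significant through the Emax contrast while the exponential contrast falls short. The significant pool drops that model; the all-five pool keeps it.

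**Step 3: how often.** Share of trials with a significant trend in which fewer than five models are significant (fixed contrasts, Firth logits, 3,000 trials per scenario):

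| Top rate | Emax 5 | Emax 100 | Linear | Sigmoid | Exponential |
|---|---|---|---|---|---|
| 25% | 68% | 55% | 86% | 97% | 99.6% |
| 30% | 56% | 27% | 66% | 91% | 98% |

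Contrast weighting matters. At the 25% rate under Emax 5, all five models are significant in 32% of signal trials with fixed contrasts, but in about 11% with contrasts recomputed per dataset. The pools therefore differ in 100 − 32 = 68% or 100 − 11 = 89% of such trials. For the other four shapes, recomputed contrasts bring the share with different pools down to roughly 40% to 56%.

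**Step 4: how much the curve moves.** The same simulated data were averaged under both rules with gAIC weights. The gap is the largest absolute difference in response rate over eight doses from 0 to 200 mg, in trials where the pools differ (fixed contrasts, 25% and 30% top rates):

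- median of the maximum gap: 0.2 to 0.7 points
- 95th percentile of the maximum gap: 0.4 to 1.4 points for four shapes, and 5.1 to 6.3 points for Emax 5
- 95th percentile at the studied doses: at most 0.7 points at 40 mg and 0.5 at 100 mg

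With one common pool this gap is zero by construction.

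**The case against.** The strongest defence has three parts.

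**There may be a technical reason.** Under multiple imputation the significant set can vary across the 200 datasets, so a fixed pool gives one well-defined quantity to combine. LOCF and non-responder imputation yield a single dataset, to which the protocol's rule applies directly. This is plausible, but the SAP does not say it. It would justify all five models under imputation; it would not justify a different pool in the analysis meant to be compared with it.

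**No test is affected.** The dose-response claim rests on the MCP step, where the largest statistic "exceeds the critical value at the one-sided 0.05 alpha". The pairwise tests and the min test do not use the Mod curve. This stands in full.

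**The shift is usually small and can be separated.** Both pools are explicit, so an all-five LOCF curve can be run at any time. This also stands. It limits the point to clarity and pre-specification.

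Some stronger readings are tempting. A reader might infer that every sensitivity analysis is affected; the tipping-point, homogeneity and ITT+MI analyses are not. Missing-as-non-response was never a one-change comparison for the primary endpoint, because SAP 5.2.3 defines it as a separate estimand with its own rule for treatment discontinuation. A reader might also take the steep Emax shape as the protocol's expected one. Protocol 4.3.1 says only that an Emax shape might be likely and gives no ED50, and the candidate set contains two Emax shapes.

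**Conclusion.** The inconsistency is in the text and is worth correcting, as a minor point. The main estimator's pool departs from Protocol 9.1 and 9.4.1.1 without a record of it. The LOCF curves use a different pool from the main curve, although SAP 5.2.2.2.2 describes only a missing-data change.

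The two rules select different model sets in a large share of signal-positive trials, but the fitted curve typically moves by less than 1 percentage point. A shift of 5 to 6 points appears only in the upper tail under Emax with ED50 5, and not at 40 or 100 mg.

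A reader might infer that a difference between the main and LOCF curves could never be attributed to missing data, or that the dose-response conclusion is in doubt. Neither follows: the pool effect is usually small and can be isolated, and the trend test is the same under both rules.

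The textual mismatch rests on no assumption. The sizes rest on the assumed zero-cell correction, gAIC weights, parameter bounds and contrast weighting; the gap sizes were obtained with fixed contrasts.

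**What to change.** Choose one of two routes:

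- Apply the main estimator's all-five pool to the LOCF and ITT+LOCF curves (SAP 5.2.2.2.2, 5.2.2.3.1.2, 5.3.2.2.1, 5.3.2.3.2) and, for consistency, to the missing-as-non-response curves (5.2.3.1.1, 5.3.2.3.4). State the pool explicitly where the significant-models sentence now stands.
- Keep the significant-model curve in those sections, which preserves the protocol's rule there, and report an all-five curve beside it.

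Under either route, add a sentence to the SAP recording that the main estimator's all-five pool departs from Protocol 9.1 and 9.4.1.1, with the reason. If the reason is that the significant set varies across imputations, say so.

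The cost is a small text change or one extra curve per section. No data collection, test or alpha allocation changes.

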5.2.2.2.3. Sensitivity Estimator 3 For the Main Estimand (Tipping Point)

For this sensitivity estimator 3, the same statistical model (MCP-Mod, stratum-adjusted MH test), data included and approach to control the Type I error rate will be used as for the main estimator (Section 5.2.2.1). The assumption for missing data and the rule to handle missing data have changed.

5.2.2.2.3.1. Assumptions

- Missing Data for HBV RNA, ALT, and HBsAg are Missing Not at Random (MNAR)
- The treatment effect is homogeneous across strata

5.2.2.2.3.2. Missing Data Handling Rule

For sensitivity estimator 3, the tipping point approach with the exhaustive scenario's analysis will be applied.

Instead of imputing non-response for missing data, the following method will be utilized to vary the imputation of response for missing data. For participants with missing response data at Week 48, responder status will be imputed in an increasing manner by participant count for each treatment group. Specifically, for each participant with missing primary endpoint at Week 48, a responder/non-responder status will be imputed starting with the scenario where all participants

are non-responders up to the scenario where all participants are responders. This would include all possible scenario combinations of responder/non-responder status for all missing data, including scenarios where participants on any active Arm have worse outcomes than participants on placebo+placebo+NA. Within the exhaustive scenarios list, the ‘worst case scenario’ will be one of the cases where all participants with missing Week 48 data in the active regimen arms will be imputed to ‘non-responders’ and all participants with missing data at Week 48 in the placebo+placebo+NA arm will be imputed to “responders”. For each scenario, the same statistical model (MCP-Mod, stratum-adjusted MH test), will be used as for the main estimator of pairwise comparisons (Section 5.2.2.1.1.2). will be performed. A graphical display of the p-values for the different hypotheses testing will summarize the results across all scenarios for this sensitivity estimator 3.

5.2.2.3. Supplementary Estimators of the Main Estimand

Supplementary analyses to better interpret the primary analysis results will be conducted by constructing additional estimators for the main estimand of the primary endpoint as defined in Section 5.2.2. This estimator will be based on the ITT set (instead of mITT).

To provide a comprehensive interpretation of the study results and the impact of COVID-19 pandemic, the following supplementary estimator will utilize the ITT analysis set.

